WPAI				Х		Х			Х	Х		
 
Will only be assessed in participants who enroll after the sentinel cohort (ie, the first 60 participants) as available.
 
See Section 8.1.5.2.
 

Visit Identifier	Screening	Baseline	Day 3	Day 5	Day 10	Day 14	Day	Day	LT	F/U	ЕТ	Notes
Abbreviations used in this table	Servening	(Day 1)	Dujo	Duy 5	2 19 10	24914	21	34		Week	(prior	1.000
may be found in Appendix 12.									12	24	to Day	
											34)	
Visit Window	Day -1 to	0 days	±1 day	±1 day	±1 day	±2	±2	±3	±7		±5 days	
	Day 1					days	days	days	days	days		
EQ-5D-5L		Х		Х		Х		Х	X	Х		
 
Will only be assessed in participants who enroll after the sentinel cohort (ie, the first 60 participants) as available.
 
See Section 8.1.5.3.
 

Staff review of study diary		Х	Х	Х	Х	Х	Х	Х			Х	• See Section 8.1.1.
Participant-completed study intervention log		Day 1 th	rough D	ay 5/6								
 
Study intervention log should be completed daily on Days 1 through Day 6 if only 1 dose was administered on Day 1.
 
See Section 6.4.
 

Record COVID-19-related medical visits				X	Х	Х	Х	X				
 
COVID-19-related medical visits a participant has attended since the last assessment will be collected.
 
See Section 8.1.2.
 

Retrieval of unused study intervention and empty study intervention containers				Х		[X]		[X]			Х	
 
If the Day 5 visit is conducted prior to last dose of study intervention, the study intervention log, empty study intervention containers, and unused study intervention should be returned at the next in-person visit.
 
See Section 6.4.
 

Study intervention accountability				X		[X]		Х			X [if needed]	
 
Study intervention accountability is only performed at the Day 14 visit if the participant administered treatment after the Day 5 visit was conducted. If the Day 14 visit is not an in-person visit, study intervention accountability will then be performed during the Day 34 visit.
 
See Section 6.4.
 

Contraception check		Х		Х	Х	Х	Х	Х			Х	• See Section 5.3.1.
Vital status check									Х	Х	Х	
Long-term follow-up telemedicine interview									Х	Х		
 
Staff will ask participants if they are experiencing COVID-19 signs and symptoms and conduct a vital status check.
 

CONCOMITANT TREATME	NT(S)											

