### 7.2. Participant Discontinuation/Withdrawal From the Study

A participant may withdraw from the study at any time at his/her own request. Reasons for discontinuation from the study include the following:

- Refused further study procedures;
- Lost to follow-up;
- Death;
- Study terminated by sponsor.

At the time of discontinuing from the study, if possible, an early discontinuation visit should be conducted. See the SoA for assessments to be collected at the time of study discontinuation and follow-up and for any further evaluations that need to be completed.

The early discontinuation visit applies only to participants who are enrolled/randomized and then are prematurely withdrawn from the study. Participants should be questioned regarding their reason for withdrawal.

If a participant withdraws from the study, he/she may request destruction of any remaining samples taken and not tested, and the investigator must document any such requests in the site study records and notify the sponsor accordingly.

If the participant withdraws from the study and also withdraws consent (see Section 7.2.1) for disclosure of future information, no further evaluations should be performed and no additional data should be collected. The sponsor may retain and continue to use any data collected before such withdrawal of consent.

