## 8.1.2. COVID-19-Related Medical Visit Details

Details of participants' COVID-19-related medical visits (ie, hospitalization, practitioner's office, home healthcare services, telemedicine, urgent care, emergency room ≤24h, extended

care facility stay) will be collected during study visits, including level of care (ICU status) and dates of utilization, including admission and discharge, as applicable.

Hospitalization is defined as >24 hours of acute care, in a hospital or similar acute care facility, including Emergency Rooms or temporary facilities instituted to address medical needs of those with severe COVID-19 during the COVID-19 pandemic. This includes specialized acute medical care unit within an assisted living facility or nursing home. This does not include hospitalization for the purposes of public health and/or clinical trial execution.

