## 9.3.2. Primary Endpoint(s)/Estimand(s) Analysis

The primary efficacy analysis will be conducted using the mITT population.

The cumulative proportion of participants hospitalized for the treatment of COVID-19 or dying during the first 28 days of the study will be estimated for each treatment group using the Kaplan-Meier method to take account of losses to follow-up and summarized graphically for each treatment group. The estimand is then the difference of the proportions in the 2 groups and its 95% CI will be presented, as well as, the associated Wald Test. For the 95% CI, the corresponding estimate of the standard error is computed using Greenwood's formula. The Greenwood's formula to estimate the variance of the difference of proportions at Day 28 is [Var(SPF(28)) + Var(SPlacebo(28))]. Instead of dealing with S(ti) the log-log approach to CI will be used. The 95% CI will be computed for the estimate of  $L(t) = \log(-\log(S(t)))$ , the log hazard function.

The CI will be in the right range when transformed back to  $S(t) = \exp(-\exp(L(t)))$ . Antilogging this CI will give a 95% confidence interval for the difference itself.

The above primary analysis will be conducted for the planned interim analysis as well. Twosided 95% CI (adjusted for the planned interim analysis) and associated p-value for the null hypothesis of no difference between treatment groups will be presented. Significance level will be determined using the O'Brien-Fleming approach at the interim analysis and the final analysis. The overall significance level is set at 5% (2 sided).

For participants who complete Day 28 assessment (Day 34), they will be censored at their last visits. For participants who discontinue before Day 28 assessment or are lost to follow up, they will be censored at the last known date in the study.

The secondary analysis associated with primary endpoint will be conducted using the mITT2 population set.

Supplemental analyses will be performed to the primary efficacy endpoint:

- 1. An analysis in the mITT analysis set of the primary endpoint where participants that received a therapeutic COVID-19 mAb treatment post-baseline will be considered as an event for the endpoint (in addition to hospitalization for COVID-19 and death due to any cause) with mAb treatment date as the time of event.

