## **Events NOT** Meeting the AE Definition

- Any clinically significant abnormal laboratory findings or other abnormal safety assessments that are associated with the underlying disease, unless judged by the investigator to be more severe than expected for the participant's condition.
- The disease/disorder being studied or expected progression, signs, or symptoms of the disease/disorder being studied, unless more severe than expected for the participant's condition.
- Medical or surgical procedure (eg, endoscopy, appendectomy): the condition that leads to the procedure is the AE.
- Situations in which an untoward medical occurrence did not occur (social and/or convenience admission to a hospital).
- Anticipated day-to-day fluctuations of preexisting disease(s) or condition(s) present or detected at the start of the study that do not worsen.

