6. ANALYSES AND SUMMARIES

6.1. Primary Endpoint

6.1.1. Primary Endpoint/Estimand Analysis

6.1.1.1. Main Analysis

The primary endpoint is proportion of participants with COVID-19 related hospitalization or death from any cause through Day 28 in the mITT population. The cumulative proportion of participants hospitalized for the treatment of COVID-19 or death during the first 28 days of the study will be estimated for each treatment group using the Kaplan-Meier method to take account of losses to follow-up and summarized graphically for each treatment group.

The estimand is then the difference of the proportions in the 2 treatment groups and its 95% confidence interval will be presented, as well as, the associated two-sample proportion test. For the 95% CI, the corresponding estimate of the standard error is computed using Greenwood's formula (Kalbfleisch and Prentice; 1980). The Greenwood's formula to estimate the variance of the difference of proportions at Day 28 is $[Var(S_{PF}(28)) + Var(S_{Placebo}(28))]$. Instead of dealing with $S(t_i)$ we will use the log-log approach to CI. The 95% CI will be computed for the estimate of L(t) = log(-log(S(t))), the log hazard function.

$$Var(\hat{L}(t)) = Var[log(-log(\hat{S}(t)))]$$

The CI will be in right range when we transform back to $S(t) = \exp(-\exp(L(t)))$. Antilogging this confidence interval will give a 95% confidence interval for the difference itself.

The above primary analysis will be conducted for the planned interim analyses as well. Two-sided 95% CI (adjusted for the planned interim analyses) and associated p-value (two-sample proportion test) for the null hypothesis of no difference between treatment groups will be presented. Significance level will be determined using the O'Brien-Fleming approach at the interim analysis and the final analysis. The overall significance level is set at 5% (2 sided).

For participants who complete Day 28 efficacy assessment (Day 34 visit), they will be censored at their last visits. For participants who discontinue before Day 28 assessment or are lost to follow-up, they will be censored at the last known date in the study.

Participants will be analysed under the mAb stratum assigned at randomization/baseline.

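### The Early Termination visit does not schedule the question that records COVID-19 hospitalizations, so a few primary events could be missed; one mark in the schedule closes the gap

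*Protocol*

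**What the plan says.** **Where hospitalization is recorded.** Protocol 8.1.2 states that details of COVID-19-related medical visits "will be collected during study visits, including level of care (ICU status) and dates of utilization, including admission and discharge, as applicable". It also gives the endpoint definition: "Hospitalization is defined as >24 hours of acute care, in a hospital or similar acute care facility". In the Schedule of Activities (SoA, Protocol 1.3) one row carries this collection, with the note "COVID-19-related medical visits a participant has attended since the last assessment will be collected". It is marked at Days 5, 10, 14, 21 and 34. Week 12, Week 24 and ET (prior to Day 34) are blank.

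**What ET does collect.** The same schedule marks supplemental oxygen, diary review, contraception, vital status, prior and concomitant medications, adjunctive procedures and AE/SAE monitoring at ET.

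**Withdrawal.** Protocol 7.2 asks for an early discontinuation visit where possible and defers to the schedule for its content: "See the SoA for assessments to be collected at the time of study discontinuation".

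**Censoring.** Under SAP 6.1.1.1, participants who discontinue before the Day 28 assessment or are lost to follow-up are event-free up to a censoring point: "they will be censored at the last known date in the study". Protocol 9.3.2 has the same rule.

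**The concern.** Hospitalization is expected to supply most of the primary events. When a participant withdraws through an ET visit, the last known date is normally that visit. The time since the previous marked visit then enters the Kaplan-Meier estimate as event-free, although the question that would establish this was not scheduled. Kaplan-Meier censoring allows for events after the censoring date. It cannot restore one that happened before that date and was never recorded.

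Death is covered at ET by the vital status check, so only the hospitalization component is exposed.

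The secondary count of COVID-19-related medical visits uses the same row and sits in the Hochberg family (SAP 5.1). Its model takes days of data collection as the offset (SAP 6.2.12). Office, telemedicine and short emergency-room visits would generally not be SAEs, so the SAE route gives this endpoint little protection. If the days up to ET count in the offset while visits in that interval go unrecorded, the rate is understated.

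**Working it through.** **1. The time left uncovered.** Nominal gaps between marked visits are 10 − 5 = 5, 14 − 10 = 4, 21 − 14 = 7 and 34 − 21 = 13 days. The SoA windows make the marked visits Days 4–6, 9–11, 12–16, 19–23 and 31–37. An ET visit that falls inside one of these may coincide with a marked visit. The clearest exposure within the endpoint period is therefore after the Day 21 visit, on Days 24–28.

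**2. A case that follows the plan as written.** A participant is seen on Day 21, is hospitalized on Days 23 to 25, and withdraws with an ET visit on Day 27.
- Day 27 lies outside the Day 21 and Day 34 visit windows, so the ET column applies and the medical-visits question is not scheduled.
- SAP Appendix 2.1 would label Day 27 as Day 34 for reporting (Days 25–37). That labels data already collected and does not cause the question to be asked.
- Unless another record shows the admission, the participant is censored event-free at Day 27.
- The missing-data sensitivity analysis (SAP 6.1.1.1) does not help. It applies only to loss to follow-up and imputes an event only when the last data precede Day 21.
- The completers analysis (SAP 6.1.1.2) keeps someone with under 28 days in the study only if an event is already recorded.

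**3. The plan's own figure.** Inputs from Protocol 9.5: 7% against 3.5%, 90% power, two-sided 5%; allocation 1:1 (Protocol 4.1). A two-proportion calculation with pooled null variance and no continuity correction gives 852 per arm, 1704 in total, within 1% of the stated 1717. With n = 1717/2 = 858.5 per arm,

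power = Φ{[d − 1.96 √(2p̄(1−p̄)/n)] / √([p₁(1−p₁)+p₂(1−p₂)]/n)} = Φ{[0.035 − 1.96 × 0.010765]/0.010732} = Φ(1.295) = 0.902.

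Expected events are 858.5 × 0.07 = 60.1 on placebo and 858.5 × 0.035 = 30.0 on active, about 90.

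**4. Events exposed at the design rates.** The 5% dropout is the plan's figure. The rest is assumed: all dropouts leave through an ET visit, they have events at their arm's design rate, every one of those events falls in the unasked interval, and no other record catches any.
- Dropouts: 0.05 × 858.5 = 42.9 per arm, 85.9 in total.
- Missed: 42.9 × 0.07 = 3.0 on placebo and 42.9 × 0.035 = 1.5 on active, 4.5 in total.
- Observed rates, as simple proportions: 0.07 × 0.95 = 6.65% and 0.035 × 0.95 = 3.33%, a difference of 3.33 points.
- Power: Φ{[0.03325 − 1.96 × 0.010507]/0.010476} = Φ(1.208) = 0.887.

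The plan appears to place dropout on top of 1717, since 1717/0.95/(0.80 × 0.75) = 3012, close to its 3000. Taking 5% of 1717/0.95 = 1807 gives 90.4 dropouts and 90.4 × 0.0525 = 4.7 missed events, so the answer hardly moves.

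**5. Range over the assumptions.** The multiplier scales the dropouts' event rate relative to design. The share is the part of their events that falls in the unasked interval and is not captured elsewhere. The documents give neither.

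| Multiplier | Share | Missed events | Observed rates | Power |
|---|---|---|---|---|
| 1 | 25% | 1.1 | 6.91% / 3.46% | 0.899 |
| 1 | 100% | 4.5 | 6.65% / 3.33% | 0.887 |
| 2 | 100% | 9.0 | 6.30% / 3.15% | 0.868 |
| 4 | 100% | 18.0 | 5.60% / 2.80% | 0.825 |

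The lower rows combine a raised event rate with total failure of every other route. They show sensitivity and are not a forecast.

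**The case against.** **Other records at ET would surface most admissions.** Inpatient hospitalization is an SAE criterion, and doubtful cases are to be treated as serious (Protocol 10.3.2). The SAE wording, admission usually with an overnight stay, is generally broader than the endpoint's 24 hours, so it tends to over-capture. Appendix 3 does exclude "The disease/disorder being studied or expected progression, signs, or symptoms of the disease/disorder being studied" from AEs, but that sentence goes on to except anything more severe than expected. Because participants expected to need hospital within 48 hours are not enrolled (exclusion criterion 2), a later admission can well meet that exception. Section 8.3.7, where a carve-out of disease-related events would sit, is marked not applicable. Oxygen support at ET extends to support received in hospital (8.1.4).

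**The text may already include ET.** Section 8.1.2 says details "will be collected during study visits" and does not exclude ET. SAP Appendix 1 says all collected data are used. The CRF and the endpoint derivation are not in these documents.

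**Few people are exposed.** Stopping treatment alone keeps a participant in follow-up (7.1). Loss requires withdrawal from the study, an ET visit, an admission since the last marked visit, and a miss by every other record.

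**What stands.** These points shrink the concern considerably, and they rule out the stronger inference that hospitalizations are simply not captured at withdrawal. They do not remove it. Section 8 makes adherence to the SoA a requirement, so a general phrase in 8.1.2 does not reliably fill a blank cell. Neither document says that SAE, oxygen or concomitant-treatment records feed the primary endpoint or are reconciled with its definition.

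**Conclusion.** The gap is real but narrow. Following the plan as written leaves the dedicated hospitalization question unasked for the final interval of anyone who withdraws through an ET visit, and the recovery routes have no stated link to the endpoint. At 5% dropout and design event rates the loss is at most about 4 to 5 of about 90 events, even with no SAE capture, and power stays at about 0.89 or above. With SAE capture working, it would be smaller.

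A reader might infer that the primary result is biased in favour of the drug. The documents do not support that. They give no withdrawal pattern by arm, so the direction is unknown. If more placebo events were lost, the difference would be attenuated, which is conservative for a superiority claim. Larger losses, up to 18 in the table, need event rates among dropouts that the documents do not state.

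This is a cheap improvement of minor severity. For the count of medical visits the SAE back-up is weaker, and the documents do not allow that loss to be sized.

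**What to change.** 1. Mark the medical-visits row at the ET (prior to Day 34) visit, using the same form and the same look-back to the previous assessment as at the scheduled visits, with admission and discharge dates.
2. For participants already withdrawn, reconcile reported SAE hospitalizations with the 8.1.2 definition. Staff blinded to arm should do this before unblinding.

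The cost is a few minutes per ET visit and a small blinded data review. Sample size and significance level do not change.

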# 2. INTRODUCTION

PF-07321332, a potent and selective SARS-CoV-2 3CL protease inhibitor, is being investigated as an oral antiviral treatment of COVID-19.

# 2.1. Study Rationale

The purpose of this study is to evaluate the efficacy and safety of PF-07321332/ritonavir for the treatment of nonhospitalized, symptomatic adult participants with COVID-19 who are at increased risk of progressing to severe illness.

# 2.2. Background

In December 2019, COVID-19 was identified as a new, potentially fatal, respiratory infection caused by the novel coronavirus, SARS-CoV-2. The WHO declared COVID-19 a Public Health Emergency of International Concern on 30 January 2020 and further characterized the disease outbreak as a pandemic on 11 March 2020. As of June 2021, at least 171,776,210 cases have been confirmed worldwide, and at least 3,693,623 deaths have occurred.

COVID-19 manifests as a wide range of illness, from asymptomatic infection to severe pneumonia, ARDS, and death. Although most (approximately 80%) cases are asymptomatic or mild, patients who are hospitalized with COVID-19 may have significant morbidity and mortality, and are at increased risk of developing complications such as severe inflammation associated with elevations in proinflammatory cytokines, ARDS, acute cardiac injury, thromboembolic events, hypercoagulability, and/or kidney injury. Moreover, other comorbidities, such as hypertension, obesity, and diabetes, as well as older age and male sex increase the risk for worse outcomes.

Although there are symptomatic and/or supportive treatments for COVID-19, few antiviral drugs are available or in late-stage development to help treat COVID-19 in patients with mild to moderate COVID-19. Existing compounds, such as hydroxychloroquine and lopinavir/ritonavir, have been evaluated as potential treatment options for COVID-19, but have not demonstrated benefit or efficacy beyond the SOC. The FDA has approved IV remdesivir, an antiviral drug with activity against SARS-CoV-2, for hospitalized patients with COVID-19. However, remdesivir monotherapy may not be sufficient in all subsets of patients across the COVID-19 spectrum or has shown modest effects. Favipiravir is currently under investigation for its activity against SARS-CoV-2 due to its broad-spectrum activity against various RNA viruses and has been approved in India and Russia to treat mild to moderate COVID-19. Although favipiravir has been generally well tolerated in clinical studies primarily for the treatment of the influenza virus, teratogenic findings in multiple animal species at exposures comparable to those achieved with the dosage regimen to treat influenza have limited its clinical use.

Three IV-administered mAb based regimens have received EUA for treatment of COVID-19 in the outpatient setting for high risk persons on the basis of observed reductions in hospitalizations and deaths in placebo-controlled randomized controlled trials.

Eligibility for mAbs is limited to persons meeting EUA-defined criteria of being at high risk for progression to severe COVID-19 or hospitalization, may only be administered in settings in which health care providers have immediate access to medications to treat a severe infusion reaction and require patients be monitored during administration and for at least 1 hour after infusion is complete. In addition, as the mAb based regimens primarily target the variable spike protein, there is ongoing risk that the continued emergence of SARS-CoV-2 variants will negatively impact the efficacy of mAb based regimens.

There is thus a high unmet need for antiviral agents that could be used for the treatment of nonhospitalized persons with COVID-19. Such agents, particularly those that target highly conserved viral targets, don't require administration in a healthcare setting, and with a risk/benefit profile supportive of administration to a broad patient population will significantly add to the treatment armamentarium for COVID-19.

The coronavirus 3CL protease is a virally encoded enzyme that is critical to the SARS-CoV-2 replication cycle, analogous to other obligatory virally encoded proteases (eg, HIV Protease, HCV Protease). Mutagenesis experiments with other coronaviruses and picornaviruses that are related to SARS-CoV-2 (picornavirus-like supercluster) have demonstrated that the activity of the 3CL protease (or the corresponding picornaviral 3C enzyme) is essential for viral replication. No close human analogs of coronavirus 3CL enzymes are known, suggesting that appropriate 3CL inhibitors may function as selective inhibitors of SARS-CoV-2 and other coronaviruses as therapeutic agents.

PF-07321332, a potent and selective inhibitor of the SARS-CoV-2 3CL protease, is being developed as an oral treatment in patients with COVID-19.

In this study, PF-07321332 will be coadministered with ritonavir. Ritonavir is a strong CYP3A4 inhibitor, and is being coadministered with PF-07321332 to achieve exposures sufficient to suppress viral replication through the entire dosing interval (ie, Ctrough>EC90). Ritonavir is not expected to have any antiviral activity against the SARS-CoV-2 virus.

